At the first visit (Day 1), subjects will complete the informed consent. A pregnancy test will be administered to women of childbearing potential, and the site physician or study site personnel will confirm subject eligibility criteria. Following this, the site physician or study site personnel trained in the use of *REDCap Cloud* will assist each subject in creating a *REDCap Cloud* account and completing the baseline assessment (Appendix 1). The first visit (Day 1) will assess important baseline information, including demographics, chronic pain classification, cannabis experience, concomitant medications, treatment goal, and ST treatment regimen. Subjects will complete the Brief Pain Inventory-Short Form (BPI-SF) and Euro- Quality of life Assessment (EQ5DL) at this visit.

At each subsequent physician-verified visit (a total of 4), the site physician or study site personnel will assist with the completion of physician follow-up assessment (Appendix 2) via *REDCap Cloud*, and reassess ST treatment regimen, concomitant medications, effectiveness and tolerability of the ST treatment regimen (including AEs & SAEs). Subjects will complete the BPI-SF, EQ5DL, and Patient Global Impression of Change (PGI-C) and physicians will complete the Clinical Global Impression-Improvement (CGI-I).

Four subject-verified follow-up assessments will be completed by subjects via the *REDCap Cloud* online portal (Appendix 3). Subjects will receive an automated email one week prior and the day of subject-verified follow-up with a reminder to complete the online assessment. The subject-verified online assessment will include questions about their ST treatment regimen, additional cannabis consumption, numeric rating scale (NRS) pain items of the BPI-SF, the EQ5D-5L, and the PGI-C.

Spontaneous AE reporting will be entered in *REDCap Cloud* by the subject during subject follow-up assessments, using the Subject AE log (Appendix 3). Physicians will verify and assess all AEs entered at physician follow-ups, using the Physician AE form (Appendix 2). All serious adverse events will be sent directly to Canopy Growth's Global Pharmacovigilance Department (GPVD) in real-time, where they will be reviewed with respect to country specific regulatory requirements. All non-serious adverse events will be sent in a monthly report to GPVD.

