4.1 Study Medication Prescribing/Authorization

Medical cannabis is accessible to subjects via different authorization or prescription pathways, in different regional jurisdictions. Authorization and prescription are the two most common pathways.

In Canada, Spectrum Therapeutics products are authorized via the physician specifying the amount (in grams) of THC and/or CBD, and the subject is free to choose the product, licensed producer, and formulation on their own. Likewise, subjects have the freedom to switch from one product or producer to another, at will.

In other countries, such as Germany, medical cannabis products are prescribed, and physicians are specific in this process regarding parameters such as the licensed producer, mode of administration, and cannabinoid content (THC:CBD).

This protocol does not assign a specific intervention. The prescription of medical cannabis is decided by the subject and his or her physician prior to enrolling the subject in the study. The principal investigator has no control over the prescribing/authorization or administration of the cannabis product.

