4.2 Study Medication: Cannabinoid Content Calculation

On entering study medication information into *REDCap Cloud*, the preprogrammed algorithm will calculate the intake amount of mgs of THC and CBD for all formulations, and whether it was inhaled or ingested. Only limited data exist on the plasma concentration of circulating cannabinoids and their metabolites resulting from inhalation of cannabis products. It is known that factors influencing this include, but are not limited to, pattern of smoking or vaping (length of inhalation), as well as the flower combustion temperature. It is possible that these data may be calculated in retrospect (unlike other formulations that will allow for real time mg calculation), if more structured studies are conducted to evaluate the cannabinoid intake from smoked and/or vaped products, from different flower varieties.

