7. OUTCOME ASSESSMENTS

7.1 Study Endpoints

Primary endpoints

- Physician selection of Spectrum Therapeutics (ST) medical cannabis treatment regimen and changes over time in:
 - (1) average daily dose of THC and CBD (in mg);
 - (2) route of administration (inhaled or ingested).

Secondary endpoints

- Subject selection of ST treatment regimen and changes over time in:
 - (1) average daily dose of THC and CBD (in mg);
 - (2) route of administration (inhaled or ingested).
- Change in BPI-SF responses from baseline.
- Change in EQ5D-5L responses from baseline.
- PGI-C for the target treatment goal.
- CGI-I for the target treatment goal.
- In subjects taking an opioid, changes in opioid use over time (calculated as milligram morphine equivalents [MME]/day).
- Among subjects taking other medication, total daily dose change over time.

Safety endpoint

- Incidence of AEs stratified by product and formulation.

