Yellow (examples include Tweed CBD Softgels)	 inhalations  	 mL  	 sprays  	 capsules  	 capsules  
Spectrum Clear (or White)		 mL  			

You indicated that your patient has been recommended an inhaled format. Please identify their most common method of administration.

(inhal_admin)

[Branching logic exists]

- Smoked
- Dried flower vaporizer (e.g. Stroz and Bickel, PAX)
- Extract vaporizer (e.g. vape pen cartridge)

Do you or your patient know the temperature set point of the vaporizer (in °C)

(inhal_vape_Y/N)

[Branching logic exists]

- Yes
- No

If known, please provide the temperature set point of your patient's vaporizer (in °C) _____

(inhal_vape_temp)

(125 / 300)

[Branching logic exists]

Calculated, approximated total daily dose of THC and CBD (in mgs)

	THC	CBD
Inhaled	
(inhal_THC)
  
View Equation
	
(inhal_CBD)
  
View Equation

Ingested	
(ingest_THC)
  
View Equation
	
(ingest_CBD)
  
View Equation

Patient reported outcomes

BPI

Throughout our lives, most of us have had pain from time to time (such as minor headaches, sprains, and toothaches). Have you had pain other than these everyday kinds of pain today?

- Yes
- No

Please select the number (0= no pain, 10= pain as bad as you can imagine) that best describes your pain at its worst in the last 24 hours.

- 0
- 1
- 2
- 3
- 4
- 5
- 6
- 7
- 8
- 9
- 10

Please select the number (0= no pain, 10= pain as bad as you can imagine) that best describes your pain at its least in the last 24 hours.

- 0
- 1
- 2
- 3
- 4
- 5
- 6
- 7
- 8
- 9
- 10

Please select the number (0= no pain, 10= pain as bad as you can imagine) that best describes your pain on the average.

- 0
- 1
- 2
- 3
- 4
- 5
- 6
- 7
- 8
- 9
- 10

Please select the number (0= no pain, 10= pain as bad as you can imagine) that best describes how much pain you have right now.

- 0
- 1
- 2
- 3
- 4
- 5
- 6
- 7
- 8
- 9
- 10

Please select the number (0= does not interfere, 10= completely interferes) that best describes how, during the past 24 hours, pain has interfered with your: **General Activity**

- 0
- 1
- 2
- 3
- 4
- 5
- 6
- 7
- 8
- 9
- 10

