Appendix 2 – PHYSICIAN-VERIFIED FOLLOW-UP ASSESSMENT

ST Regimen Canada

[figure not shown]
[figure not shown]

[figure not shown]
[figure not shown]

[figure not shown]
[figure not shown]

[figure not shown]
[figure not shown]

Please enter in the table below total daily amount of Spectrum Therapeutics products consumed. Please be conscious of the units provided:

Inhaled cannabis = total number of inhalations per day

Ingested oils = total mL per day

Spray format = total number of sprays per day

Capsules & edibles = total number of capsules or total number of chocolate bar squares per day

Physician-recommended Regimen of Spectrum Therapeutics Products					
	Inhaled Formats (dried flower, extract vaporizers) -- report daily total number of inhalations	Ingested Oil Formats - report daily total number of mLs	Spray Formats - report daily total number of sprays	Low Potency Capsule & Edible Formats - report daily total number of low-potency capsules (i.e. 2.5 mg), number of chocolate bar squares, etc.	High Potency Capsule Formats - report daily total number of high-potency capsules
Red (examples include Spectrum #1-4; Tweed Bakerstreet, Highlands, Houdstooth, Donegal; LBS Sunset)	 inhalations  	 mL  	 sprays  	 capsules  	 capsules  
Orange	 inhalations  		 sprays  		
Purple (examples include LBS Ocean View)	 inhalations  		 sprays  		
Blue (examples include Tweed Penelope)	 inhalations  	 mL  	 sprays  	 capsules  	 capsules  
Green (examples include Tweed Argyle)	 inhalations  	 mL  	 sprays  	 capsules  	 capsules  
Yellow (examples include Tweed CBD Softgels)	 inhalations  	 mL  	 sprays  	 capsules  	 capsules  
Spectrum Clear (or White)		 mL  			

You indicated that your patient has been recommended an inhaled format. Please identify their most common method of administration.
(*inhal_admin*)
[Branching logic exists]

- Smoked
 Dried flower vaporizer (e.g. Stroz and Bickel, PAX)
 Extract vaporizer (e.g. vape pen cartridge)

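### The visible Canadian regimen forms ask for the amount consumed but label it as the physician's recommendation, so entries behind the physician-selection primary endpoint may hold either quantity

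*Protocol*

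**What the plan says.** Section 7.1 defines the primary endpoint as "Physician selection of Spectrum Therapeutics (ST) medical cannabis treatment regimen and changes over time in" daily THC and CBD dose in mg and route (inhaled or ingested). A secondary endpoint is "Subject selection of ST treatment regimen and changes over time in" the same two measures. The two endpoints differ only in whose selection is recorded.

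The regimen is entered in a table on the ST Regimen Canada pages of Appendices 1, 2 and 3. All three carry the instruction "Please enter in the table below total daily amount of Spectrum Therapeutics products consumed". In Appendices 2 and 3 the heading of that table describes it as the regimen recommended by the physician. In all three, the item that follows an inhaled entry begins "You indicated that your patient has been recommended an inhaled format".

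Section 4.2 says that "the preprogrammed algorithm will calculate the intake amount of mgs of THC and CBD for all formulations". Section 4.1 describes the Canadian pathway: "products are authorized via the physician specifying the amount (in grams) of THC and/or CBD", while "the subject is free to choose the product, licensed producer, and formulation on their own". Of the home form, Section 3.1 says: "The subject-verified online assessment will include questions about their ST treatment regimen, additional cannabis consumption".

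**The concern.** What the physician recommends and what the subject uses are two different quantities, and the protocol gives each its own endpoint. The visible form does not settle which one is wanted. A physician who follows the instruction above the table reports use; one who follows the table's heading reports the recommendation. Both entries pass through the same calculation into the same derived mg fields.

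At stake is the meaning of the primary endpoint. If some entries are use and others are recommendation, the result reported as physician selection is a mixture. The change-over-time part is exposed as well: if a physician enters the plan at baseline and use at follow-up, the apparent change in prescribing includes a change in what was recorded.

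**Working it through.** The protocol gives no figure to reproduce on this point, so the check sets the texts side by side.

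**1. What each visible Canadian form says about the same table**

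| | Appendix 1 (physician, baseline) | Appendix 2 (physician, follow-up) | Appendix 3 (subject, at home) |
|---|---|---|---|
| Instruction | consumed | consumed | consumed |
| Table heading | none visible naming the physician's recommendation | physician-recommended | physician-recommended |
| Follow-on item | recommended | recommended | recommended |
| Derived fields | one set: THC and CBD, inhaled and ingested | one set | one set |

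Counts: instruction in terms of consumption 3 of 3; follow-on item in terms of recommendation 3 of 3; heading in terms of recommendation 2 of 3. No visible form has a second table or a marker separating the two quantities.

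**2. Can one reading reconcile the wording?**

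- If the physician forms are meant to record the recommendation, the instruction in Appendices 1 and 2 is wrong. The heading in Appendix 3 does not suit a form meant for the subject's own regimen.
- If they are meant to record use, the heading in Appendix 2 and the follow-on item are wrong, and the primary endpoint becomes reported use.

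Either way some printed text has to change. Appendix 3 has a further slip: its follow-on item addresses a physician about a patient, although Section 3.1 has subjects answer about their own regimen.

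**3. Can the two quantities differ?** By Section 4.1, yes, in Canada. The physician specifies an amount of THC and/or CBD and the subject chooses product and formulation. Formulation determines whether the product is inhaled or ingested, so route can differ as well as dose.

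**4. How often are these forms used?** Table 1 schedules the regimen item at 5 physician visits (baseline and months 2, 4, 8, 12) and 4 home follow-ups (months 1, 3, 6, 10), 5 + 4 = 9 in all. Appendix 2 serves 4 of the 5 physician visits. Appendices 2 and 3 together serve 4 + 4 = 8 of the 9 scheduled entries. This counts where the conflicting wording appears, not how many entries are wrong.

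**5. What is not visible?** In the regimen sections, 1 figure (Appendix 1), 8 (Appendix 2) and 4 (Appendix 3) are not shown: 1 + 8 + 4 = 13. Appendix 4 refers to a question on whether the patient still takes the products, and Table 1 lists an item on additional cannabis consumption. Neither appears on the visible forms, which are therefore incomplete, and a separate recommended-regimen field cannot be ruled out.

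**6. Size of any bias.** Not computable. The protocol gives no ratio of used to recommended amount.

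**The case against.** The strongest defence is that the protocol already separates physician-verified from subject-verified collection, and that this is the natural source of the primary and secondary endpoints. That is a plausible intention. It tells us who answered, however, not which quantity was entered, and the physician form itself asks for consumption under a recommendation heading.

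A second objection is that the harm depends on unseen content. This stands as a limit: the statement that a later analysis could not tell the two apart holds only if no separate field exists. It does not remove the conflict, because instruction, heading and follow-on item are printed text about one table and a hidden field would not make them agree.

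Third, Appendix 1 is weak evidence. It shows no recommendation heading, and a subject new to these products has consumed nothing on Day 1, so the entry would most naturally be the planned regimen. That is accepted. The ambiguity bears mainly on follow-up and on subjects already using the products.

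Fourth, the word intake in Section 4.2 describes a unit conversion rather than an endpoint. It deserves alignment but carries little weight alone.

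A reader might also infer that the table cannot accommodate the Canadian pathway, because its cells are organised by product colour and format while the physician may specify only an amount. The protocol does not support treating that as an error. Inclusion criterion 3 requires a prescription or authorisation for a Spectrum Therapeutics product, and the Synopsis has physician and subject complete the regimen item together. Product and format can therefore normally be known at entry, and nothing in the protocol requires a regimen without them to be recordable.

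**Conclusion.** The point holds as an internal inconsistency that should be fixed. On the visible Canadian follow-up forms the text contradicts itself on whether recommended or used regimen is entered. Appendix 1 has the weaker form of the same conflict. Since this distinction alone separates the primary endpoint from its secondary counterpart, the physician-form entry may hold either quantity.

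The conclusion rests on two conditions: that no separate field for the recommended regimen exists in content not visible here, and that recommended and used regimens do differ for some subjects, as Section 4.1 allows. Under those conditions an SAP, which was not available for this review, could define the endpoint but could not recover which quantity had been typed.

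It would go too far to infer that the primary endpoint is biased in a known direction, or that the problem affects the whole registry. The number of affected entries and the size and direction of any bias are unknown, and only the Canadian forms can be judged.

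**What to change.** 1. On the physician forms (Appendices 1 and 2), make the instruction, table heading and follow-on item all ask for the regimen the physician recommended or authorised. If use is also wanted there, record it in a separately labelled field.
2. Relabel Appendix 3 as the amount and route the subject used, and remove the reference to the physician's recommendation and the wording addressed to a physician about a patient.
3. Align the term intake in Section 4.2 and the endpoint wording in Section 7.1 with these labels.
4. If a separate recommended-regimen field already exists in content not visible here, correct only the labels.

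Cost: changed label text on three eCRF pages, small wording changes in Sections 4.2 and 7.1, at most one extra set of fields, and a little entry time at physician visits. No additional subjects or visits are needed.

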7.2.6 Other Concomitant Medications

Physicians will confirm subjects who take any non-opioid concomitant medication for pain at baseline, or who start it during the study, and will be asked to report the medication type. The following medication categories have been identified as common medication classes taken by chronic pain patients: Nonsteroidal Anti-inflammatory Drugs (NSAIDs) and Acetaminophen, Antidepressants, Anticonvulsants, Benzodiazepines and Muscle Relaxants. Physicians will be asked to report the medication type and total daily dose, and any changes throughout the study.

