- Irritability
- Stress

Please indicate the type of sleep disruption that best describes that which is the primary focus of the patient's primary treatment goal

- Increase daytime alertness
- Increase sleep quality or quantity

Please indicate the type of function that best describes that which is the primary focus of the patient's primary treatment goal

- Activities unrelated to employment (e.g. leisure activities)
- Employment related activities (e.g. return to work full time)
- Improve relationships

Concomitant medication

Is your patient currently taking an of the following classes of prescription medication (select all that apply)

- Nonsteroidal Anti-inflammatory Drugs (NSAIDs) and Acetaminophen
- Antidepressants (TCA, SNRI, SSRI)
- Anticonvulsants (gabapentin, pregabalin)
- Muscle Relaxants
- Benzodiazepines
- Opioids
- Other
- Medical Cannabis from a Licensed Producer other than Spectrum

NSAIDs and Acetaminophen Dosing Information

Name of drug

Daily dose of [baseline_visit][nsaid1_name] (total mg per day)

- Check to add additional NSAID /Acetaminophen medications

Name of drug

Daily dose of [baseline_visit][nsaid2_name] (total mg per day)

- Check to add additional NSAID /Acetaminophen medications

Name of drug

Daily dose of [baseline_visit][nsaid3_name] (total mg per day)

Antidepressants Dosing Information

Name of drug

Daily dose of [baseline_visit][antidep1_name](total mg per day)

Check to add additional Antidepressant medications

Name of drug

Daily dose of [baseline_visit][antidep2_name] (total mg per day)

Check to add additional Antidepressant medications

Name of drug

Daily dose of [baseline_visit][antidep3_name] (total mg per day)

Anticonvulsants Dosing Information

Name of drug

Daily dose of [baseline_visit][anticon1_name] (total mg per day)

Check to add additional anticonvulsant medications

Name of drug

Daily dose of [baseline_visit][anticon2_name] (total mg per day)

Check to add additional anticonvulsant medications

Name of drug

Daily dose of [baseline_visit][anticonvu3_name] (total mg per day)

Muscle Relaxants Dosing Information

Name of drug _____

Daily dose of [baseline_visit][musrel1_name] (total mg per day) _____

Check to add additional muscle relaxant medications

Name of drug _____

Daily dose of [baseline_visit][musrel2_name] (total mg per day) _____

Check to add additional muscle relaxant medications

Name of drug _____

Daily dose of [baseline_visit][musrel3_name] (total mg per day) _____

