Do you or your patient know the temperature set point of the vaporizer (in °C)
(*inhal_vape_Y/N*)
[Branching logic exists]

- Yes
 No

If known, please provide the temperature set point of your patient's vaporizer (in °C) _____
(*inhal_vape_temp*)
(125 / 300)
[Branching logic exists]

Calculated, approximated total daily dose of THC and CBD (in mgs)

	THC	CBD
Inhaled	(inhal_THC)  View Equation	(inhal_CBD)  View Equation
Ingested	(ingest_THC)  View Equation	(ingest_CBD)  View Equation

Concomitant medication

Concomitant medication - Existing

Existing NSAIDs and Acetaminophen Dosing Information

At last visit, you indicated that your patient was taking [baseline_visit][nsaid1_name]. Is your patient still taking this medication?

- Yes
 No

What is their current daily dose of [baseline_visit][nsaid1_name] (total mg per day)?

Please select the reason why your patient stopped taking this medication.

- Side effects
 Cost
 Lack of benefit
 No longer needs/ replaced by medical cannabis
 Unknown

At last visit, you indicated that your patient was taking [baseline_visit][nsaid2_name]. Is your patient still taking this medication?

- Yes
 No

Please select the reason why your patient stopped taking this medication.

- Side effects
 Cost
 Lack of benefit
 No longer needs/ replaced by medical cannabis
 Unknown

What is their current daily dose of [baseline_visit][nsaid2_name] (total mg per day)?

At last visit, you indicated that your patient was taking [baseline_visit][nsaid3_name]. Is your patient still taking this medication?

- Yes
 No

Please select the reason why your patient stopped taking this medication.

- Side effects
- Cost
- Lack of benefit
- No longer needs/ replaced by medical cannabis
- Unknown

What is their current daily dose of [baseline_visit] [nsaid3_name] (total mg per day)?

Existing Antidepressants Dosing Information

At last visit, you indicated that your patient was taking [baseline_visit][antidep1_name]. Is your patient still taking this medication?

- Yes
- No

Please select the reason why your patient stopped taking this medication.

- Side effects
- Cost
- Lack of benefit
- No longer needs/ replaced by medical cannabis
- Unknown

What is their current daily dose of [baseline_visit] [antidep1_name] (total mg per day)?

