- No longer needs/ replaced by medical cannabis
- Unknown

What is their current MME?

Existing Other Medications Dosing Information

At last visit, you indicated that your patient was taking other medications, including [baseline_visit][othmed_name]. Is your patient still taking any of these other prescription medications?

- Yes
- No

Please describe any **changes** to their other existing prescription medications since last visit (including changes to total daily dose)

Concomitant Medications - New

Since last visit, has your patient **started** taking any of the following classes of prescription medication (select all that apply)

- Nonsteroidal Anti-inflammatory Drugs (NSAIDs) and Acetaminophen
- Antidepressants (TCA, SNRI, SSRI)
- Anticonvulsants (gabapentin, pregabalin)
- Muscle Relaxants
- Benzodiazepines
- Opioids
- Other
- Medical Cannabis from a Licensed Producer other than Spectrum

Name of new NSAID/Acetaminophen medication (started since last visit)

Daily dose of [physician_1st_follow][nsaid4_name] (total mg per day)

Name of new antidepressant medication (started since last visit)

Daily dose of [physician_1st_follow][antidep4_name] (total mg per day)

Name of new anticonvulsant medication (started since last visit)

Daily dose of [physician_1st_follow][anticon4_name] (total mg per day)

Name of new muscle relaxant medication (started since last visit)

Daily dose of [physician_1st_follow][musrel4_name] (total mg per day)

Name of new benzodiazepine medication (started since last visit)

Daily dose of [physician_1st_follow][benzo4_name] (total mg per day)

Please enter MME (total daily morphine equivalent dose in mg)

Name of new prescription medication (started since last visit, not covered in above classes)

Daily dose of [physician_1st_follow][othmed4_name] (total mg per day)

Physician AE form

Product information

Do you have any adverse events to report related to this patient?

- Yes
- No

Suspect product(s) name

Start date

_____ (YYYY-MM-DD)

End date

_____ (YYYY-MM-DD)

Route of administration

- oral - oil
- oral - softgel
- oral - spray
- oral - beverage
- oral - chocolate
- oral
- inhalation - smoked
- inhalation - vaporized
- inhalation

Dose (please include amount and unit i.e. mg, ml, #softgels, #inhalations, etc.)

Did reaction disappear after reducing the dose or stopping the product ?

- No
- Yes
- Unknown

Did reaction reappear after same product/treatment was restarted?

- No
- Yes
- Unknown

AE description

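### As printed, the physician follow-up form re-asks only baseline drugs, so a non-opioid drug added during the study has no dose field after the visit that first records it, and the class questions leave out non-prescription drugs that Section 7.2.6 covers

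*Protocol*

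**What the plan says.** Section 7.1 lists total daily dose change over time, among subjects taking other medication, as a secondary endpoint. Section 7.2.6 covers any non-opioid pain drug taken at baseline or begun during the study, and states: "Physicians will be asked to report the medication type and total daily dose, and any changes throughout the study".

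Section 3.1 says "At each subsequent physician-verified visit (a total of 4), the site physician or study site personnel will assist with the completion of physician follow-up assessment" and identifies that assessment as Appendix 2. No other physician follow-up form is listed.

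In Appendix 2, the existing-medication items for NSAIDs/acetaminophen, antidepressants, anticonvulsants, muscle relaxants and benzodiazepines follow one pattern: "At last visit, you indicated that your patient was taking [baseline_visit][nsaid1_name]. Is your patient still taking this medication". The name comes from the baseline record, slots 1 to 3 in each class. The new-medication block has one name per class ("Name of new NSAID/Acetaminophen medication (started since last visit") and one dose ("Daily dose of [physician_1st_follow][nsaid4_name] (total mg per day"), stored in slot 4. The stop reasons are side effects, cost, lack of benefit, a combined option for no longer needed or replaced by cannabis, and unknown.

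The baseline class question in Appendix 1 is "Is your patient currently taking an of the following classes of prescription medication". The new-medication question in Appendix 2 has the same restriction to prescription drugs.

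**The concern.** The existing-drug items refer to the last visit but draw on baseline. The two are the same only at month 2. At month 4 a drug that was started before month 2 is neither a baseline drug nor one started since the last visit, so the printed form has nowhere to put its dose, a change in its dose, or its stop. Baseline drugs, by contrast, are followed to month 12, and their stops and reductions are recorded at every visit.

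If class totals are formed by summing the recorded doses, a replacement is seen as the old drug going away without the new one staying. In an uncontrolled registry that also asks whether cannabis replaced the drug, such a pattern could be taken for a medication-sparing effect. Doses that were never collected cannot be recovered in the analysis.

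**Working it through.** The protocol states no figure on this point, so there is nothing to reproduce. The check traces the printed form through the schedule.

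**Inputs.** Physician visits are at baseline and months 2, 4, 8 and 12 (Section 3.1). Existing items read baseline slots 1–3, and the new item reads slot 4 at the visit after the start (Appendix 2). Three things are assumed for illustration: baseline drug A and new drug B are each 1 unit, the form is used unchanged at all four follow-ups, and the recorded total is the sum of the doses that have a field.

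**Equal-dose replacement of A by B.** The true total is 1, 1, 1, 1, 1. The recorded total is A while it is taken, plus B at its first visit only.

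| Swap made | M0 | M2 | M4 | M8 | M12 |
|---|---|---|---|---|---|
| before M2 | 1 | 1 | 0 | 0 | 0 |
| M2 to M4 | 1 | 1 | 1 | 0 | 0 |
| M4 to M8 | 1 | 1 | 1 | 1 | 0 |
| M8 to M12 | 1 | 1 | 1 | 1 | 1 |

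The total is right at the visit that first records B and wrong from the next visit on. A swap after month 8 causes no error.

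**Add-on before month 2, A kept.** True 1, 2, 2, 2, 2; recorded 1, 2, 1, 1, 1. B has a field at 1 of 4 follow-ups and none at the other 3.

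**Class mean at month 12.** If a share s of users swap at equal dose by month 8 and nobody else changes, with swappers on average doses, the recorded mean is (1 − s) of the true one, so the apparent change is −s. Assumed values of 5%, 10%, 20% and 30% give −5%, −10%, −20% and −30% against a true change of 0. This only restates the assumed rate; the protocol gives none.

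**After the fix.** If every recorded drug is listed again at each visit, the swap gives 1, 1, 1, 1, 1 and the add-on 1, 2, 2, 2, 2. Both match the truth.

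**Opioids.** Baseline users are asked for their current MME, which is a total, so an added or swapped opioid stays in it. The existing-opioid item is tied to a baseline MME, however, so a subject who first starts an opioid before month 2 has an MME at month 2 only.

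**Same interval.** Two new drugs of one class begun between the same two visits share one slot.

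**Prescription wording.** Section 7.2.6 has no such limit; the class questions in Appendices 1 and 2 do. Non-prescription NSAIDs and acetaminophen therefore fall outside the question, and a switch from a prescribed drug to a different, non-prescribed one is recorded as a stop.

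**The case against.** The strongest objection is that the printout may be the month-2 build. The new-drug fields carry the prefix `physician_1st_follow`, and a stray label reads `anticon1_dose_follow1`. At month 2 the last visit is baseline, so the wording is correct there, and later builds could read slot 4 back. The printed appendices are also not a full record of the live system: the regimen page is shown for Canada only, and the closing text of Appendix 4 cites a question that does not appear in the text of Appendix 2. This stands as a limit on what can be claimed. It does not remove the point, because Section 3.1 assigns this form to all four visits and no later version or carry-forward rule is shown.

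A reader might infer more than the protocol supports:

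- That a medication-sparing bias is demonstrated. It is conditional on the form being used unchanged and on how totals are built, which may be set in an analysis plan that is not at hand. Section 9.3 rules out imputation in descriptive summaries unless otherwise stated; it does not say that an unasked drug counts as zero.
- That a second new drug in a class never has a field. One started in a later interval can use that visit's slot.
- That any move to non-prescription supply reads as a stop. The follow-up item names the drug, so the same drug bought without a prescription is still answered yes.
- That drugs in the other category are lost in the same way. Those listed at baseline have a free-text item for changes.

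**Conclusion.** The point holds for the form as printed and for the five named non-opioid classes. If Appendix 2 is used at months 4, 8 and 12 as Section 3.1 says, the later dose or stop of any drug added by month 8 has no field, contrary to Section 7.2.6. An equal-dose replacement made by then appears as a reduction from the visit after it is first recorded. Under simple summing this omission can only lower later totals. Its size cannot be stated, because the replacement rate is unknown and milligram doses of different drugs need not be equal. Among opioid users, only those who start after baseline are affected.

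The prescription wording is a separate contradiction with Section 7.2.6 and does not depend on which build is shown. Its direction is not fixed, since non-prescription use is outside the question at baseline as well.

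The change should be made: the endpoint is secondary, but the data cannot be recovered later.

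**What to change.** - At months 4, 8 and 12, fill the existing-medication block with every drug recorded at an earlier visit and not since stopped, including slot-4 drugs and opioids first started after baseline. If later builds already do this, print or specify them in the protocol.
- Allow repeated entries per class in the new-medication block, as the baseline form already does.
- Add a stop reason for replacement by another drug.
- Delete the word prescription from the class questions in Appendices 1 and 2, or add a prescribed/non-prescribed tick, so that the forms collect what Section 7.2.6 describes.

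The cost is REDCap Cloud piping and wording edits and a slightly longer medication page for subjects with added drugs. No extra visits are needed.
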